### 8.1.2 Management of Side Effects of RBV (Step 2 participants with suspected relapse, virologic failure, or undefined post-treatment viremia)

The most common AE of RBV therapy is anemia due to hemolysis. Anemia typically occurs within 1 to 2 weeks of initiating RBV therapy and usually resolves within 4 to 8 weeks of drug discontinuation or dose reduction. Indirect bilirubin elevation is commonly seen in those participants with anemia secondary to RBV-induced hemolysis.

Another major side effect of RBV is its teratogenicity. It is therefore strongly recommended that pregnant women or breastfeeding women and men with pregnant sexual partners not receive RBV. Women who become pregnant on study and men on study whose partners become pregnant must discontinue study treatment and complete the discontinuation evaluations as indicated in [section 8.2](#).

RBV dosing in this study will be based on weight at Step 2 entry (see [section 5.0](#)). Dose reduction of RBV is the recommended management for RBV-associated anemia and should be performed according to the product label. Information is summarized in [Table 8.1.2-1](#). It is recommended that sites contact the A5380 CMC with questions regarding difficult anemia management and/or if it is felt RBV discontinuation is required. Participants will continue to take G/P if RBV is temporarily or permanently discontinued.

Table 8.1.2-1: Suggested RBV Dose Reduction in the Event of Anemia

Laboratory Values	Reduce RBV Dose to 600 mg/day if:	Hold RBV if:
Hemoglobin in participants with no cardiac disease	<10 g/dL	<8.0 g/dL
Hemoglobin in participants with history of stable cardiac disease	≥2 g/dL decrease in hemoglobin during any 4-week treatment period	<10 g/dL despite 4 weeks at reduced dose
Symptomatic drop in hemoglobin to be managed at the discretion of the site investigator and can be discussed with the protocol chairs.		

Reintroduction of RBV

If RBV is temporarily stopped due to anemia, the hemoglobin must be rechecked within 2 weeks and at 2-week intervals until stable. Once RBV has been withheld due to either a laboratory abnormality or clinical manifestation, an attempt may be made to restart RBV at 600 mg daily in two divided doses and further increase the dose to 800 mg daily in two divided doses. However, it is not recommended that RBV be increased to the original assigned dose. Please refer to the table below for dosing intervals.

Table 8.1.2-2: Dosing Intervals to Restart RBV

Daily Dose	Morning Dose	Evening Dose
600 mg	400 mg (2 tablets)	200 mg (1 tablet)
800 mg	400 mg (2 tablets)	400 mg (2 tablets)

NOTE A: The half-life of RBV in participants with normal renal function is 290 hours.

NOTE B: The ranges of hemoglobin values used as criteria for triggering dose reduction of RBV do not correspond to those used to grade toxicities in the DAIDS AE Grading Table, corrected Version 2.1, July 2017. Therefore, sites are expected to use specific criteria shown in Table 8.1.2-1 above.

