**Risks of Study Drugs**

The drugs used in this study may have side effects, such as headaches, fatigue, diarrhea, nausea, asthenia, pruritic skin, and abnormal liver function tests. There is a risk of serious and/or life-threatening side effects when certain non-study medications are taken with the study drugs.

Drug interactions may increase the chances of side effects, may affect the levels of ARVs or other medications and/or cause changes in liver enzymes and other abnormal blood tests. Certain HIV medications may be changed to reduce this risk. For certain HMG-CoA reductase inhibitors (statins), others may require dose adjustment or careful monitoring. For digoxin, the dose should be reduced and closely monitored while on G/P. Drug interactions that lower the levels of glecaprevir or pibrentasvir may decrease the participant's chances for a cure of hepatitis C and/or select for drug resistance. Certain drugs known to cause lower levels of glecaprevir or pibrentasvir will be avoided.

Some people with HCV and HBV coinfection receiving DAA therapy for HCV, have experienced reactivation of HBV. Some of these cases have led to severe hepatitis, liver failure and death. This has been reported mostly in individuals who are positive for HBsAg and extremely rarely in those who appear to have resolved HBV infection by lab tests. Those with HBsAg will be excluded, while those with resolved HBV infection will be monitored.

Ribavirin may be used in Step 2 for those with detection of viremia after 4 weeks of glecaprevir/pibrentasvir in Step 1. The most common AE of RBV therapy is anemia due to hemolysis. Anemia typically occurs within 1 to 2 weeks of initiating RBV therapy and usually resolves within 4 to 8 weeks of drug discontinuation or dose reduction. Indirect bilirubin elevation is commonly seen in those participants with anemia secondary to RBV-induced hemolysis.

Another major side effect of RBV is its teratogenicity. It is therefore strongly recommended that pregnant women or breastfeeding women and men with pregnant sexual partners not receive RBV. Women who become pregnant on study and men on study whose partners become pregnant must discontinue study treatment and complete the discontinuation evaluations as indicated in [section 8.2](#).

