##### Premature Treatment Discontinuation Evaluations

The A5380 CMC must be informed, as soon as possible, when a participant comes off study treatment due to an AE. Participants who permanently discontinue study treatment for toxicity or any other reason, and who have not met the HCV virologic failure criteria below, will also follow the schedule in [Table 6.1-2](#). If applicable, additional or more frequent post-treatment toxicity follow-up may be determined by the site PI.

Participants who prematurely discontinue study treatment (i.e., prior to completion of the last dose of G/P per the assigned dosing period) will complete the premature treatment discontinuation evaluations. Participants will then follow the post-treatment schedule in [Table 6.1-2](#).

NOTE: In Step 2 where applicable: If G/P is discontinued, participants should discontinue RBV. Under no condition should the participant remain on RBV monotherapy. In contrast, participants who discontinue RBV in Step 2 can continue G/P to complete their planned G/P regimen.

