### Pregnancy Outcomes and Reporting

If a woman has completed the study or chooses to discontinue from the study before the end of the pregnancy, then site staff should request permission to contact her regarding pregnancy outcomes at the end of pregnancy. If the information is obtained, pregnancy outcomes will be submitted on an eCRF at the end of the pregnancy.

Pregnancy will result in immediate discontinuation of the study drugs and initiation of counseling regarding the lack of information of safety in pregnancy with G/P and for those in Step 2 receiving RBV, regarding the teratogenicity of RBV. Participants who become pregnant while on study will be followed on study/off treatment until study completion. A visit 6 months following the end of pregnancy will be conducted for evidence of AEs in the participant and infant, and an outcome eCRF will be completed.

In Step 2, male participants taking RBV whose partners become pregnant will undergo treatment discontinuation and remain on study for continued follow-up until the end of the study. They will receive counseling on RBV teratogenicity and the same follow-up visit at 6 months after their partners' delivery as outlined for pregnant women. This same risk of teratogenicity is not seen with G/P, thus pregnancy of female partner in Step 1 is not an indication for treatment discontinuation.

All participants including female partners of male participants who become pregnant while taking the study treatment will have their pregnancy reported to AbbVie via the sponsor.

If a female participant or male participant with a pregnant female partner has completed the study or chooses to discontinue from the study before the end of the pregnancy, site staff should request permission to contact the female participant or male participant with a pregnant female partner regarding pregnancy outcomes at the end of pregnancy. If the information is obtained, pregnancy outcomes will be submitted on an eCRF at the end of the pregnancy.

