## 9.0 CRITERIA FOR DISCONTINUATION

### 9.1 Premature Treatment Discontinuation

- Drug-related toxicity (see [section 8.1](#)).
- Pregnancy in a female participant.
- Participant request to discontinue for any reason.
- Requirement for prohibited concomitant medications (see [section 5.4](#)).
- Breastfeeding.
- Clinical reasons believed life threatening by the physician, even if not addressed in the toxicity section of the protocol.
- For Step 2 only: Pregnancy in female partner of a male participant taking RBV.
- HCV virologic failure during Step 2 (see [section 6.2.6](#)).

NOTE: It is important to determine whether the treatment discontinuation is primarily due to an AE, lack of efficacy, or other reason.

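### The rule for a male participant whose partner becomes pregnant is worded more broadly in Protocol 2.3 and 8.1.2 than in 8.2 and 9.1, and for Step 2 men on G/P plus RBV it is not stated whether G/P also stops

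*Protocol*

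**What the plan says.** Five parts of the Protocol bear on a man whose female partner becomes pregnant.

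- **Section 2.3, Risks of Study Drugs**, in a paragraph on RBV teratogenicity: "Women who become pregnant on study and men on study whose partners become pregnant must discontinue study treatment".
- **Section 8.1.2, Management of Side Effects of RBV**, repeats the sentence: "men on study whose partners become pregnant must discontinue study treatment". The same section later says, in its paragraph on RBV dosing and anemia: "Participants will continue to take G/P if RBV is temporarily or permanently discontinued".
- **Section 8.2, Pregnancy Outcomes and Reporting**: "In Step 2, male participants taking RBV whose partners become pregnant will undergo treatment discontinuation and remain on study". It adds that G/P does not carry the same teratogenic risk, "thus pregnancy of female partner in Step 1 is not an indication for treatment discontinuation".
- **Section 9.1**, in the list of reasons for premature treatment discontinuation: "For Step 2 only: Pregnancy in female partner of a male participant taking RBV".
- **Section 6.2.6**, in a note on stopping one drug but not the other: "participants who discontinue RBV in Step 2 can continue G/P to complete their planned G/P regimen".

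Section 5.0 supplies the vocabulary. Study treatment in Step 1 is G/P. In Step 2, study-provided treatment is G/P with or without RBV.

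**The concern.** The sentence in 2.3 and 8.1.2 is mandatory and, on its words, reaches every man in the study and all of his study treatment. Sections 8.2 and 9.1 reach only Step 2 men on RBV. A site that reads one pair of sections gets a wider rule than a site that reads the other.

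A second question arises inside the narrower rule. For a man on G/P plus RBV, 8.2 and 9.1 end *treatment* but do not name the drugs. The reason given is specific to RBV, and other text treats stopping RBV as compatible with going on with G/P.

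At stake is whether a man being re-treated after a failed first course finishes his G/P, and whether sites act alike in a safety-related situation. The re-treatment SVR12 (Section 10.2.3.5) would reflect whichever action the site took.

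**Working it through.** No arithmetic decides this point and the plan gives no figure to reproduce. The check is to apply each passage to each kind of man. Regimens and durations are from Section 5.1.1.

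| Man with a pregnant partner | 2.3 and 8.1.2, as worded | 8.2 and 9.1 | General text in 8.1.2 and 6.2.6 on stopping RBV |
|---|---|---|---|
| Step 1, G/P for 4 weeks | Stops G/P | No stop: 8.2 says so expressly, and 9.1 lists the event for Step 2 only | Not relevant, no RBV |
| Step 2, regimen 2A, G/P for 8 weeks | Stops G/P under 2.3 (2A is for re-infection, which the heading of 8.1.2 does not name) | Not listed | Not relevant, no RBV |
| Step 2, regimen 2C, G/P for 16 weeks | Stops G/P | Not listed | Not relevant, no RBV |
| Step 2, regimen 2B, G/P plus RBV for 16 weeks | Stops study treatment, which includes G/P | *Treatment* stops, drugs not named | If RBV is the drug stopped, G/P continues (8.1.2) or can continue (6.2.6) |

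Reading across the rows:

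1. **Step 1.** The literal words of 2.3 and 8.1.2 conflict with 8.2. The conflict has an answer in the text, because 8.2 addresses this exact case and 9.1 agrees with it.
2. **Step 2 without RBV.** The literal words again conflict with the narrower list in 9.1. Here 8.2 gives no express exemption, since the one it states is for Step 1. The answer comes only from these men being absent from 8.2 and 9.1.
3. **Step 2 with RBV.** All four sections agree that something stops. They do not settle what. Read with Section 5.0, 2.3 and 8.1.2 take G/P with it. Sections 8.2 and 9.1 are silent on the drugs. The statements in 8.1.2 and 6.2.6 that G/P goes on, or may go on, after RBV make no exception for a partner's pregnancy.

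Size for one man: if the pregnancy becomes known t weeks into a G/P course of D weeks, the readings differ by D − t weeks of G/P. At t = 0 the upper limit is 16 weeks for regimen 2B (D = 16).

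The letters of amendment (#1 to #4) and clarification memos (#1 to #3) were checked. None changes 2.3, 6.2.6, 8.1.2, 8.2 or 9.1 on this point, or the description of study treatment in 5.0.

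**The case against.** The best reply is context. Both broad sentences follow directly on the teratogenicity of RBV. Section 8.1.2 manages RBV side effects in Step 2, and Section 2.3 has just introduced RBV as a Step 2 drug. Both refer the reader to 8.2, although only for the discontinuation evaluations. A reader who takes 8.2 and 9.1 as the specific text will find them consistent with each other and limited to men on RBV.

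Most of this stands for Step 1. It stands less well for Step 2 men on G/P alone. The heading of 8.1.2 names failure categories that include men on regimen 2C, and the entry criteria exclude men with pregnant partners in both steps without any RBV condition (4.2.18, 4.3.7, 4.4.15), so the broad wording is not absurd on its face. Context does not help with regimen 2B, because there the question is what *treatment* covers.

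Two stronger readings are tempting and are not supported.

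- A reader might infer that the Protocol contains a third written rule, under which a partner's pregnancy stops RBV and leaves G/P running. No passage says that. It is an inference from the recommendation against RBV for these men together with the general text on RBV discontinuation. The sentence in 8.1.2 belongs to the anemia paragraph, and the one in 6.2.6 is permissive.
- A reader might infer that the primary SVR12 result is at risk because Step 1 courses would be cut short. A site would have to set aside the express statement in 8.2 and the list in 9.1 to do that.

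The case is also rare by design. Men with pregnant partners are excluded at entry to each step, contraception is required in both (4.1.12, 4.3.8), and the trial enrolls 44 to 50 participants, of whom only those with recurrence or failure can enter Step 2.

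**Conclusion.** The concern holds as a contradiction of wording plus one real gap. Sections 2.3 and 8.1.2, taken at their words, contradict 8.2 and 9.1 on which men must stop. For Step 1 the documents answer the question themselves. For Step 2 men on G/P plus RBV they do not say whether G/P stops with RBV.

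For a man in that last group the readings run from none to all of his remaining G/P. Across the trial the effect is likely very small. The documents give no expected number of such men, so that judgement rests on the entry exclusions, the contraception requirement and the small Step 2 population. Sample size, alpha, power and the primary analysis do not change. Re-treatment SVR12 is listed among the other outcome measures and lies outside the Primary SAP.

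The conclusion assumes that *study treatment* in 2.3 and 8.1.2 carries the meaning given in Section 5.0. For Step 2, that section defines the slightly different term of study-provided treatment. It is still worth correcting, because this is a mandatory stopping rule and the reading changes what a participant receives. No view is taken on which rule is right.

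**What to change.** Issue a clarification memo that reconciles Sections 2.3, 6.2.6, 8.1.2, 8.2 and 9.1. For the pregnancy of a male participant's partner, one rule should state:

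1. which step or steps it applies to;
2. whether it depends on the man taking RBV, with Step 2 men on G/P alone named explicitly;
3. whether *treatment* means RBV only or RBV and G/P, and so whether the general text in 8.1.2 and 6.2.6 on G/P after RBV applies to this event.

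State the rule once and have the other sections refer to it. The sponsor must decide which rule applies.

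The cost is wording only. The point itself calls for no change to sample size, endpoints, visit schedule or the Primary SAP.

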#### Step 2 (8-16-week duration)

Any participant who experiences viral re-infection, suspected relapse, virologic failure, or undefined post-treatment HCV viremia will proceed to Step 2 for re-treatment. Based on both the classification of recurrence and the site PI preference, participants proceeding to Step 2 will be placed on one of the following re-treatment regimens:

Participants with viral re-infection will be re-treated with regimen 2A.

- Regimen 2A:  
Glecaprevir 100 mg/pibrentasvir 40 mg FDC tablet to be taken as 3 tablets orally once daily with food for 8 weeks.

For participants experiencing virologic relapse, virologic failure, or undefined post-treatment HCV viremia (not otherwise defined as re-infection, relapse, or virologic failure), re-treatment options are either regimen 2B or 2C.

- Regimen 2B:  
Glecaprevir 100 mg/pibrentasvir 40 mg FDC tablet to be taken as 3 tablets orally once daily with food, plus RBV 200 mg tablets taken orally twice daily with food. RBV is to be dosed per [Table 5.1.1-1](#) (Weight-based RBV Dose) and [Table 5.1.1-2](#) (Renal Dosing for RBV) with renal dosing superseding weight-based dosing as applicable. Treatment duration is 16 weeks.
- Regimen 2C:  
Glecaprevir 100 mg/pibrentasvir 40 mg FDC tablet to be taken as 3 tablets orally once daily with food for 16 weeks.

The site PI may choose to re-treat these participants with an alternative SOF-based triple DAA regimen in accordance with the local standard of care. The re-treatment regimen choice will be made by the site PI upon discussion with the A5380 CMC. All products for alternative regimens, except for glecaprevir/pibrentasvir, will need to be obtained locally by the site outside of the

study. An example that may use both study product and non-study product is defined in Regimen 2D. Additional possible DAA regimens to be considered for Step 2 can be found in the A5380 MOPS.

- Regimen 2D:  
Glecaprevir/pibrentasvir plus an appropriate third locally-sourced HCV DAA product for a minimum of 12 weeks, administered in accordance with manufacturer's package insert and per site clinician's discretion. The HCV DAA product selected by the site PI must be discussed with A5380 CMC prior to therapy initiation.

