For study products provided through the study in regimens 2A-2D, a new prescription must be provided to the site pharmacist at Step 2 initiation that includes the Step number, PID, and SID. If participant is being prescribed RBV, the prescription must also include weight (kg) and CrCl.

Table 5.1.1-1: Weight-based RBV Dose

Weight (kg)	Morning Dose	Evening Dose
<75 kg	600 mg (3 tablets)	400 mg (2 tablets)
≥75 kg	600 mg (3 tablets)	600 mg (3 tablets)

The total RBV daily dose has been divided into two doses. The dose of RBV will be based on participant's weight at Step 2 entry or at confirmation visit. Changes in weight after Step 2 entry do not require a change in dose. Doses will only be changed for toxicity management.

For Step 2 participants with reduced CrCl, RBV can be dosed based on Table 5.1.1-2 below.

Table 5.1.1-2: Renal Dosing for RBV

Creatinine Clearance	RBV Dose
30-50 mL/min	Alternating doses, 200 mg (1 tablet) daily alternating with 400 mg (2 tablets) daily
Less than 30mL/min and Hemodialysis	200 mg (1 tablet) daily

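### The ribavirin anemia steps in Protocol section 8.1.2 fit only weight-based doses; for participants on the renal dose, 600 mg/day is no reduction and the 600-then-800 mg restart exceeds the assigned dose

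*Protocol*

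**What the plan says.** Regimen 2B in Protocol section 5.1.1 combines G/P with RBV dosed by weight (Table 5.1.1-1) or by renal function (Table 5.1.1-2), "with renal dosing superseding weight-based dosing as applicable". At CrCl 30-50 mL/min the renal table reads "Alternating doses, 200 mg (1 tablet) daily alternating with 400 mg (2 tablets) daily"; below 30 mL/min or on hemodialysis the dose is 200 mg daily. Letter of Amendment #1 reworked the rows of this table and kept the amounts. No Step 2 criterion sets a CrCl limit; the laboratory entry criterion specific to RBV (4.3.5) is hemoglobin alone.

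Section 8.1.2 covers anemia. It states that "RBV dosing in this study will be based on weight at Step 2 entry". Table 8.1.2-1, titled "Suggested RBV Dose Reduction in the Event of Anemia", has one reduction column, "Reduce RBV Dose to 600 mg/day if", and one hold column. In the row for stable cardiac disease the hold trigger is "<10 g/dL despite 4 weeks at reduced dose". After a hold, "an attempt may be made to restart RBV at 600 mg daily in two divided doses and further increase the dose to 800 mg" daily, although "it is not recommended that RBV be increased to the original assigned dose". Table 8.1.2-2 gives the tablets for the two restart doses. No renal exception appears in the section, and no memo or letter in the documents changes it.

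**The concern.** The 600 and 800 mg steps make sense only if the starting dose is 1000 or 1200 mg/day. The protocol expressly provides for a group whose starting dose is far lower, and for them three things go wrong.

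1. **Restart.** Taken as written, a participant whose RBV was just held for anemia could restart on more than the assigned dose, while the same paragraph advises against returning even to that dose.
2. **Reduction.** The only reduced dose in the table lies above every renal dose, so it cannot serve as a reduction. It should not be read as an instruction to increase; the table is only suggestive and defers to the product label.
3. **Cardiac hold trigger.** In the stable-cardiac row, holding RBV depends on time spent at a reduced dose, and the table defines none for these participants.

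The protocol names hemolytic anemia as the most common adverse event of RBV and lowers the dose when CrCl is reduced. An anemic participant on a renal dose is therefore one for whom the dosing instruction should be clear.

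**Working it through.** **Inputs**

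- Weight-based dose (Table 5.1.1-1): 600 + 400 = 1000 mg/day below 75 kg; 600 + 600 = 1200 mg/day at 75 kg or more.
- Renal dose (Table 5.1.1-2): (200 + 400)/2 = 300 mg/day on average at CrCl 30-50, with a highest single day of 400 mg; 200 mg/day at CrCl below 30 or on hemodialysis.
- Steps in section 8.1.2: 600 mg/day (reduction target and first restart dose) and 800 mg/day (second restart dose). Table 8.1.2-2 reproduces these: 400 + 200 = 600 and 400 + 400 = 800.

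**Ratio of each step to the assigned dose** (step divided by assigned daily dose)

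| Assigned dose | 600 mg/day | 800 mg/day |
|---|---|---|
| 1000 mg (under 75 kg) | 0.60 (-40%) | 0.80 (-20%) |
| 1200 mg (75 kg or more) | 0.50 (-50%) | 0.67 (-33%) |
| 300 mg mean (CrCl 30-50) | 2.00 (+100%) | 2.67 (+167%) |
| 400 mg, highest renal day | 1.50 (+50%) | 2.00 (+100%) |
| 200 mg (CrCl <30 or hemodialysis) | 3.00 (+200%) | 4.00 (+300%) |

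The steps work in the first two rows and fail in the other three. In absolute terms the reduction target is 600 - 300 = 300 mg/day above the CrCl 30-50 mean, and 600 - 200 = 400 mg/day above the lowest renal dose.

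**How many people could be affected**

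The documents give no rates for RBV uptake, reduced CrCl or anemia, so the following are assumptions, multiplied as if independent: 5-20% of 44 participants need re-treatment; 25-75% of those get RBV; 1-10% of those have CrCl of 50 mL/min or less; 10-30% of those reach any anemia trigger, and 1-10% are held.

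- Any trigger, low: 44 × 0.05 × 0.25 × 0.01 × 0.10 = 0.00055 people.
- Any trigger, high: 44 × 0.20 × 0.75 × 0.10 × 0.30 = 0.198 people. The per-person probability is 0.0045, so the chance of at least one is 1 - (1 - 0.0045)^44 = 0.180, or 1 - (1 - 0.0045)^50 = 0.202 at the maximum enrollment of 50.
- Hold, which must come before a restart, low: 44 × 0.05 × 0.25 × 0.01 × 0.01 = 0.000055 people.
- Hold, high: 44 × 0.20 × 0.75 × 0.10 × 0.10 = 0.066 people. The chance of at least one is 1 - (1 - 0.0015)^44 = 0.064.

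**The case against.** The strongest reply is that section 8.1.2 shows its own scope and blocks the harmful reading. It says dosing goes by weight, and Note A quotes a half-life only for normal renal function, so a reader could infer that the steps are meant for weight-based doses. The restart is optional. The advice not to return to the assigned dose, read strictly, rules out both 600 and 800 mg for a renally dosed participant. Reduction is to follow the product label, and sites can consult the Clinical Management Committee. Symptomatic hemoglobin drops are left to the investigator. The RBV prescription must state CrCl, CrCl is recalculated on treatment, and section 5.4 requires package-insert review when a dose changes. RBV can also be avoided through Regimen 2C or a sofosbuvir-based regimen, and criteria 4.2.13 and 4.4.10 exclude significant or symptomatic cardiac disease, which narrows the cardiac-row problem further.

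Most of this stands as a reason to expect little harm. It does not supply the missing rule. The weight sentence refers to section 5.0, which contains the renal table, so it does not limit scope. Where the ceiling rules out both restart steps, the paragraph contradicts itself and leaves the site with no restart dose. The label is invoked for reduction, not for restart, and its content is not in the documents. None of the other safeguards says which starting doses the 600 and 800 mg steps apply to.

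The objection is also right that the head counts are not firm bounds. The rates are assumed, and they may be linked: a site may avoid RBV when CrCl is low, for instance. They indicate scale only.

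**Conclusion.** The concern holds as a minor error in safety wording. For participants on the renal dose, section 8.1.2 offers no usable reduced dose and a restart at 2.0 then 2.7 times the assigned dose (CrCl 30-50, against the 300 mg/day mean) or 3.0 then 4.0 times (CrCl below 30 or on hemodialysis). These ratios come entirely from the protocol's own tables.

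The number of people exposed rests on the assumed rates above. It is a small fraction of one person, and most likely zero. Nothing in Step 1 is affected, so the primary SVR12 result does not depend on this point.

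**What to change.** State in section 8.1.2 that the 600 and 800 mg steps, in Tables 8.1.2-1 and 8.1.2-2 and in the reintroduction paragraph, apply only to participants assigned weight-based RBV. Add a row for participants dosed by Table 5.1.1-2 in which no reduced or restart dose exceeds the assigned renal dose. The protocol team should set its clinical content; one option is to hold RBV at the anemia trigger, including in the stable-cardiac row, which would also settle the undefined hold condition there.

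The cost is one sentence and one table row in the next clarification memo or letter of amendment, with no added visits, tests or participants.
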